BMI	Body mass index

KEYWORDS

COX-2, prostacyclin, ibuprofen, Vioxx, thrombosis, nitric oxide, ADMA, L-arginine

STUDY SUMMARY

TITLE COX-2/prostacyclin/ADMA/NO axis in the cardiovascular system

DESIGN Two arm, single centre mechanistic study. Subjects will be computer randomised to either arm.

AIMS

- To perform a systemic analysis of how COX-2 inhibition by celecoxib affects vascular function and 'omic biomarkers including those associated with the COX-2/prostacyclin/ADMA axis in healthy male volunteers
- To investigate how this is altered by L-arginine supplementation

OUTCOME MEASURES

Primary endpoint: endothelial function measured using EndoPAT

Secondary endpoints: Blood pressure, cardiovascular biomarkers, eicosanoid and methylarginine/amine levels, plasma proteome and blood transcriptome

POPULATION Healthy male volunteers

ELIGIBILITY

Inclusion Criteria	Exclusion Criteria

 • Male, 18-40 years old • No abnormal findings on medical history, screening, physical examination, haematology, biochemistry, urinalysis and vital signs (sitting blood pressure, resting pulse rate, respiratory rate and body temperature within two weeks of commencement date) • Normal fasting lipid profile (Soverson et al, 1994) • Non-smoking • Clear venous access in upper limbs • BMI 18-30 • No history or signs of drug abuse • No other medication 4 weeks before or during study • Informed written consent 	
 • Any history of allergy to NSAIDs or arginine • Significant medical conditions • Pulse rate<50 beats/minute • Sitting systolic blood pressure <80 or >160 mmHg • Sitting diastolic blood pressure <60 or >100 mmHg • Baseline endothelial dysfunction (as defined by EndoPAT; LnRHI<0.51) • Participation in other clinical study 8 weeks before or during study • Donation of blood 8 weeks before or during study • COVID-19 vaccination within 4 weeks • Positive COVID-19 test

TREATMENT

[figure not shown]
Celecoxib: 200 mg b.i.d (400mg total/day)

L-arginine 5g b.i.d. (10g total/day)

Celecoxib, L-arginine or placebo will be dispensed against an individual prescription by a registered pharmacist. Drugs will be stored at the Imperial/NIHR Clinical Research Facility. Drugs or placebo will be administered orally.

DURATION 7 days of active treatment in each study arm (see flowchart below)

STUDY FLOWCHART AND TIMELINE

Exam	Visit number	1	2	3	4
	0 (Screening)				
Informed consent	x				
Medical history	x				

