3. STUDY DESIGN

Two arm, single centre mechanistic study.

Forty healthy male volunteers, twenty in each arm.

Primary endpoint: Endothelial function measured using EndoPAT

Secondary endpoints: Sitting blood pressure, cardiovascular biomarkers, eicosanoid and methylarginine/amine levels, plasma proteome and blood transcriptome.

Functional Endpoints	Biomarkers

 • EndoPAT- endothelial function • Blood pressure 	
 • Methylarginines- ADMA, SDMA and L-NMMA • Amino acids- full range including L-arginine, L-ornithine, L-citrulline. • Eicosanoids- full range including prostacyclin and PGI-M • Cardiovascular Biomarkers- thromboxane, endothelin-1, nitric oxide, renin, angiotensin, apolipoproteins, D-dimer, Sicam-1 and CRP • Renal biomarkers- creatinine, urea, cystatin C, KIM-1 and albumin

Healthy male volunteers will be randomized to 7 days' treatment with celecoxib (200mg b.i.d.; the standard maximum anti-inflammatory dose) or placebo in a double blinded format. Samples and measurements will be made at baseline and after the final dose. Following a washout of at least 4 weeks, L-arginine (Lambers Healthcare Limited) may be administered in a dose of 5g b.i.d. (10g total/day) as per the study flowchart (page 5). A rational approach was taken in selecting the arginine dose since 10g/day increases plasma arginine by $\approx 40\%$ ¹⁷. At each visit, the primary endpoint will be endothelial function, measured using EndoPAT, which measures changes in flow-mediated endothelial function in the microvasculature. Importantly, EndoPAT is clinically validated with scores that correlate with cardiovascular risk¹⁸. Additionally, at each study visit, blood pressure, cardiovascular biomarkers (by ELISA) and

eicosanoid and methylarginine/amine levels (by GC/LCMS/MS) will be measured. Samples will also be collected for measurement of 'omic' biomarkers including transcriptomics, proteomics, lipidomics and metabolomics. Additionally volunteers will monitor and record their blood pressure readings daily using a home monitoring device and protocols validated and suggested (respectively) by the British and Irish Hypertension Society. In vivo aspects of this study will be performed using validated protocols¹⁵ and using facilities and staff at the NIHR/Wellcome Trust Imperial College Clinical Research Facility.

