Once participants are enrolled and randomised in the study, the study visits (visits 1 & 2 in phase 1 and visits 3 & 4 in phase 2) need to occur exactly 7 days apart. If participant attends visit 1 but is unable to attend visit 2 for a reason that is unrelated to the study medication e.g. develops an unrelated illness or cannot attend for personal reasons, the participant will have the option to re-enrol as a new participant if there is at least a 4-week washout period if they wish to do so. These participants will need to re-attend screening and re-consent and will be treated as a new participant with a new study number. To avoid double counting, any data obtained from the initial enrolment will not be used and will be superseded by the data generated by re-enrolment.

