5. ADVERSE EVENTS

Definitions

Adverse Event (AE): any untoward medical occurrence in a clinical study subject.

Serious Adverse Event (SAE): any untoward and unexpected medical occurrence or effect that:

- **Results in death**
- **Is life-threatening** – *refers to an event in which the subject was at risk of death at the time of the event; it does not refer to an event which hypothetically might have caused death if it were more severe*
- **Requires hospitalisation**
- **Results in persistent or significant disability or incapacity**
- **Is a congenital anomaly or birth defect**

Medical judgement will be exercised in deciding whether an AE is serious in other situations. Important AEs that are not immediately life-threatening or do not result in death or hospitalisation but may jeopardise the subject or may require intervention to prevent one of the other outcomes listed in the definition above, will also be considered serious.

Reporting procedures

All adverse events will be reported. Depending on the nature of the event the reporting procedures below will be followed. Any questions concerning adverse event reporting will be directed to the Chief Investigator ([name]) and the medically qualified Investigators ([name] and [name]) in the first instance.

Non serious AEs

All such events, whether expected or not, will be recorded.

Serious AEs

A SAE form will be completed and sent to the medically qualified Investigator, [name], within 24 hours. However, relapse and death and hospitalisations for elective treatment of a pre-existing condition do not need reporting as SAEs.

All SAEs will be reported to the Imperial College Research Ethics Committee where in the opinion of the Chief Investigator, the event was:

- 'related', i.e. resulted from the administration of any of the research procedures; and
- 'unexpected', i.e. an event that is not listed in the protocol as an expected occurrence

Reports of related and unexpected SAEs will be submitted within 15 days of the chief investigator/medically qualified investigator becoming aware of the event, using the NRES SAE form for non-IMP studies. The Chief Investigator will also notify the Sponsor of all SAEs.

Contact details for reporting SAEs

[contact]

CI email: [contact]

Please send SAE forms to: [name]

[contact]

[contact] (Mon to Fri 09.00 – 17.00)

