7. STATISTICS AND DATA ANALYSIS

Sample size: This is a novel mechanistic study where the primary endpoint is the effect of celecoxib on endothelial function measured using the EndoPAT device. We anticipate that we will require n=20-40 in each study arm to detect a difference based on previous work using similar drugs and alternative measurement approaches. For example Carlsson and Wennmalm (1983)¹⁹ showed a reduction in endothelial function with ibuprofen (effect size: 0.80 standard deviations) and diclofenac (effect size: 1.06 standard deviations). This equates to a power of 72-92% at n=20 and 95-100% at n=40 to detect a difference between groups at a nominal significance threshold of p<0.05. As we are using a different drug and an alternative measurement platform, power can only be estimated broadly. As such, we will perform an interim analysis of data after studying n=20 volunteers per group during the 'wash out' period. At this point, actual effect size and variance will be determined and experimental power re-calculated. If our primary endpoint is not achieved, we may revise our endpoints and/or if additional power is required, we will reserve the option to recruit up to an additional n=20 volunteers per group. Dependent upon the results the interim analysis may also serve as a stop-go checkpoint for continuation of the L-arginine arm of the study.

Data analysis: Data will be analysed according to approaches applicable to the measurement. This includes standard parametric and non-parametric tools (including Fisher's exact tests, Student's t-tests, 1-way and 2-way ANOVAs, Mann Whitney U-tests and Kruskall-Wallis tests) as well as specialised tests for large omic data sets (including modified t-test with false discovery correction where appropriate). Across all tests differences will be considered significant where p<0.05.

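### The re-enrolment rule sets aside all first-enrolment data, including exposure and adverse events, and does not protect the first allocation; it should be limited to efficacy data.

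*Combined protocol and SAP*

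**What the plan says.** The rule stands in the combined protocol and SAP, Section 4 (Participant Entry), under Re-enrolment. It applies after randomisation. Visits 1 and 2 must be exactly a week apart. A man who attends the first but cannot attend the second, because of illness or personal circumstances not connected with the study drug, may choose to come back after a washout of at least 4 weeks. He is screened and consented again and "will be treated as a new participant with a new study number". To prevent double counting, "any data obtained from the initial enrolment will not be used and will be superseded by the data generated by re-enrolment".

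Other parts of the document bear on this:

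- Study Summary, Design: "Subjects will be computer randomised to either arm".
- Study Summary, flowchart: medication is dispensed at visit 1.
- Section 3: "Forty healthy male volunteers, twenty in each arm". Treatment is celecoxib "or placebo in a double blinded format".
- Section 5, Reporting procedures: "All adverse events will be reported". Non-serious events are all to be recorded, expected or not.
- Section 8, Confidentiality: study records are kept for 10 years.

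**The concern.** The exclusion is wider than its purpose. Counting a man once in the EndoPAT analysis requires choosing one efficacy record for him. It does not require setting aside the fact that he was randomised and given study drug, or what happened to him while he may have been taking it. The rule has no exception for exposure or safety data, and it does not call for the two study numbers to be linked.

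The rule also leaves the first allocation unprotected. If a returning man is handled like any other new entrant, he may be allocated again and could receive the other treatment.

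Two things are at stake: a complete account of everyone randomised and dosed, and the principle that a man is analysed in the arm to which he was first randomised.

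**Working it through.** **The plan's own figure.** The only related figure is the power in Section 7: 72-92% at 20 per arm and 95-100% at 40 per arm, for effects of 0.80 and 1.06 SD. With the normal approximation, power = Φ(d√(n/2) − 1.96), two-sided 0.05:

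- n = 20: 0.80 × √10 − 1.96 = 0.570, giving 71.6%; 1.06 × √10 − 1.96 = 1.392, giving 91.8%.
- n = 40: 0.80 × √20 − 1.96 = 1.618, giving 94.7%; 1.06 × √20 − 1.96 = 2.780, giving 99.7%.

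The figures reproduce. The point below does not depend on them.

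**Step 1: who is covered.** The rule starts after randomisation and after visit 1. The flowchart dispenses medication at visit 1, so such a man may have taken up to a week of celecoxib or placebo.

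**Step 2: what the rule sets aside.** These data can exist from the first enrolment: the screening and visit 1 measurements, the daily home blood pressure readings (Section 3), the exposure itself, and any adverse events. The rule covers all of them.

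**Step 3: comparison with Section 5.** An adverse event is there defined as any untoward medical occurrence in a study subject, with no requirement that the drug caused it. One of the rule's two examples of a reason for missing visit 2 is an illness. An illness arising after randomisation is an adverse event under Section 5 even if unrelated. So one of the rule's own examples is an event that Section 5 wants reported and Section 4 says will not be used.

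**Step 4: comparison with the other rules for non-completers.** Section 4 (Withdrawal criteria) allows data from withdrawn men to be used. Section 8 (Consent) keeps men given alternative treatment in the study for follow-up and analysis. Only the re-enrolment rule excludes everything.

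**Step 5: allocation.** Section 4 says neither that the man is randomised again nor that he keeps his first allocation. New-participant status together with computer randomisation points to a fresh draw, but this is inferred.

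**Step 6: effect on the primary endpoint.** In phase 1, EndoPAT is measured at visit 1 (baseline) and visit 2 (after treatment). Missing visit 2 is the trigger, so no phase 1 post-treatment EndoPAT result is discarded.

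**Step 7: scale, as illustration only.** The documents give no expected number of re-enrolments, k. The table assumes k = 1 to 4, 40 completing men, and a fresh, independent 1:1 draw (the ratio is implied by 20 per arm).

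| k | First courses not used, k/(40 + k) | Chance at least one man changes arm, 1 − 0.5^k |
|---|---|---|
| 1 | 1/41 = 2.4% | 50% |
| 2 | 2/42 = 4.8% | 75% |
| 3 | 3/43 = 7.0% | 87.5% |
| 4 | 4/44 = 9.1% | 93.8% |

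The second column is the share of phase 1 courses left out of use, not out of the record. The third applies only if allocation is redrawn. Neither measures bias.

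**The case against.** The strongest reply is that the rule concerns analysis and has a sensible aim. Section 5 still requires events to be recorded and reported when they occur, with serious events on a form within 24 hours and notified to the sponsor. Later re-enrolment does not cancel those duties, and Section 8 keeps the records for 10 years. A reader might infer that the first exposure disappears from the record or that its safety information is wholly lost. The documents do not support that: what is excluded is use.

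A reader might also infer that a between-arm safety comparison is distorted. Neither the endpoints nor Section 7 plans one, so the loss is to complete reporting and participant flow.

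On efficacy, re-entry is the man's choice and requires an unrelated reason, the washout, new screening and new consent. The trial is double blind. If allocation is redrawn, the new draw is itself random; only the decision to re-enter depends on a judgement made after dosing may have begun. That a man who had received both treatments would recognise his arm is speculation.

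Most of this stands, and it limits the point. It does not explain why a rule against double counting should extend to exposure and adverse events, or why allocation is left unstated.

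**Conclusion.** The point holds as a defect in a stated rule. Followed literally, Section 4 removes first-course exposures, adverse events and first randomisations from what the trial uses, and it leaves the first allocation unprotected. It should be changed, because the rule is broader than its purpose and sits badly with Section 5.

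The size is modest. Each such man is 1/40 = 2.5% of the planned sample, and the illustrative 2.4% to 9.1% of courses rests on an assumed one to four re-enrolments. Bias in the primary comparison is probably small, since no phase 1 post-treatment EndoPAT result exists for these men, but it cannot be computed without a re-enrolment rate. It would go too far to say that men will change arm or that the primary comparison is invalid: re-randomisation is an inference, and nothing in the documents shows material bias.

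**What to change.** Amend Re-enrolment in Section 4 to:

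- limit the exclusion to the first-enrolment efficacy data;
- keep first-course exposure, adverse events and first randomisations in safety reporting and participant flow;
- link the two study numbers;
- have pharmacy re-issue the allocation from the first randomisation, under the code, with the blind intact.

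Add to Section 7 a sensitivity analysis of the primary endpoint without re-enrolled men.

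The sponsor's aim of one efficacy record per man is kept, and no extra participants or visits are needed. The cost is a few sentences, a pharmacy look-up of the earlier allocation, and one additional analysis.

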5. ADVERSE EVENTS

Definitions

Adverse Event (AE): any untoward medical occurrence in a clinical study subject.

Serious Adverse Event (SAE): any untoward and unexpected medical occurrence or effect that:

- **Results in death**
- **Is life-threatening** – *refers to an event in which the subject was at risk of death at the time of the event; it does not refer to an event which hypothetically might have caused death if it were more severe*
- **Requires hospitalisation**
- **Results in persistent or significant disability or incapacity**
- **Is a congenital anomaly or birth defect**

Medical judgement will be exercised in deciding whether an AE is serious in other situations. Important AEs that are not immediately life-threatening or do not result in death or hospitalisation but may jeopardise the subject or may require intervention to prevent one of the other outcomes listed in the definition above, will also be considered serious.

Reporting procedures

All adverse events will be reported. Depending on the nature of the event the reporting procedures below will be followed. Any questions concerning adverse event reporting will be directed to the Chief Investigator ([name]) and the medically qualified Investigators ([name] and [name]) in the first instance.

Non serious AEs

All such events, whether expected or not, will be recorded.

Serious AEs

A SAE form will be completed and sent to the medically qualified Investigator, [name], within 24 hours. However, relapse and death and hospitalisations for elective treatment of a pre-existing condition do not need reporting as SAEs.

All SAEs will be reported to the Imperial College Research Ethics Committee where in the opinion of the Chief Investigator, the event was:

- 'related', i.e. resulted from the administration of any of the research procedures; and
- 'unexpected', i.e. an event that is not listed in the protocol as an expected occurrence

Reports of related and unexpected SAEs will be submitted within 15 days of the chief investigator/medically qualified investigator becoming aware of the event, using the NRES SAE form for non-IMP studies. The Chief Investigator will also notify the Sponsor of all SAEs.

Contact details for reporting SAEs

[contact]

CI email: [contact]

Please send SAE forms to: [name]

[contact]

[contact] (Mon to Fri 09.00 – 17.00)

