1. INTRODUCTION

1.1. BACKGROUND

Cyclooxygenase-2 (COX-2) is an inducible enzyme expressed in inflammation and cancer. However, COX-2 in discreet regions including areas of the vasculature and in the kidney^{1, 2} is a powerful cardiovascular protective pathway that works via formation of prostacyclin. In blood vessels, prostacyclin acts on smooth muscle and platelets to produce vasodilation and platelet inhibition, and in the kidney, regulates renal function and vasoactive hormone pathways to indirectly affect the systemic vasculature. These cardiovascular protective roles of COX-2 and prostacyclin are illustrated by the fact that nonsteroidal anti-inflammatory drugs (NSAIDs), which work by blocking COX-2 and include some of the world's most commonly taken drugs, cause the high profile cardiovascular side effects that have led to black box warnings on all drugs in this class^{2, 3}.

It was initially thought that cardiovascular side effects were limited to drugs that selectively target COX-2³⁻⁵, such as Vioxx® (rofecoxib) and Celebrex® (celecoxib), introduced in the early 2000's^{6, 7}. However, as a result of subsequent epidemiology analyses^{8, 9} and, most recently, the publication of two large clinical cardiovascular outcome studies, SCOT¹⁰ and PRECISION¹¹, it is clear that traditional NSAIDs, including ibuprofen and naproxen, carry at least as great a cardiovascular risk as the COX-2 selective drug celecoxib with ibuprofen, which is remarkably still an over the counter medication, emerging as significantly more toxic to the kidney¹¹.

The scale of use of NSAIDs (estimated to be regularly taken by 20-30% of the population) and the degree of associated risk (increased by 30%¹²) means that these drugs are a significant risk factor for heart attacks and strokes in their own right, potentially accounting for up to 50,000 of the 458,000 heart attacks and strokes in the UK each year (Jan 2016). Moreover, we now know that this risk emerges with just 1-2 weeks of use¹³. Concern over adverse cardiovascular events caused by NSAIDs has led to cautious prescribing of COX-2 selective NSAIDs in favour of older NSAIDs, which are more toxic to the gut, or opioids, which carry problems of tolerance, addiction and additional health burdens, and to the withdrawal in Europe of celecoxib for the prevention of colon cancer.

Mediators of protection: the power of arginine as a therapy

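### The SAE definition requires an event to be unexpected, so a serious event of a known class type can miss the 24-hour form and the sponsor notice

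*Combined protocol and SAP*

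**What the plan says.** All the rules at issue are in Section 5 (Adverse Events) of the combined protocol and SAP.

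- **Adverse event (AE):** "any untoward medical occurrence in a clinical study subject". There is no condition on expectedness.
- **SAE:** "any untoward and unexpected medical occurrence or effect that" leads to one of five outcomes, among them death, threat to life and hospitalisation.
- **Medical judgement:** other important AEs can also be classed as serious. This clause has no expectedness condition, but it is written for events short of death, immediate threat to life or hospitalisation.
- **24-hour rule:** "A SAE form will be completed and sent to the medically qualified Investigator" within 24 hours.
- **Sponsor:** "The Chief Investigator will also notify the Sponsor of all SAEs".
- **Ethics committee:** SAEs are reported if the Chief Investigator judges them related and unexpected. Here *unexpected* is explained as "an event that is not listed in the protocol as an expected occurrence".
- **General rule:** "All adverse events will be reported". Non-serious events are recorded regardless of expectedness.

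Section 1.1 (Background) says of NSAIDs that they "cause the high profile cardiovascular side effects that have led to black box warnings on all drugs in this class".

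**The concern.** Seriousness describes the outcome of an event. Expectedness describes what was already known about the treatment. Section 5 puts both into the SAE definition, and every later rule that uses the term SAE inherits both. The 24-hour form and the sponsor notice have no trigger of their own.

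The layout of the section suggests a different intention: the sponsor hears of all SAEs, and the ethics committee hears of those that are related and unexpected. The two extra words in the definition cut across that.

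At stake is a serious cardiovascular event in a healthy man on celecoxib. Section 1.1 presents cardiovascular harm as known for the whole class and says that the risk appears within one to two weeks of use. Each treatment period lasts 7 days. An investigator who has read that section could reasonably call such an event expected.

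**Working it through.** No arithmetic applies, because the point depends on how the rules in Section 5 fit together.

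**Step 1. Is the second filter redundant?** If *unexpected* means the same in both places, every event that enters through the main definition is already unexpected. The ethics committee test then reduces to *related* for those events. It can screen out only events classed as serious by medical judgement. A filter that does almost no work suggests that the definition was not meant to contain the word.

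**Step 2. Is there a list of expected events?** The ethics committee bullet relies on one. None appears in the text available. The front matter and the part between Sections 8 and 10 were not available, so its absence is established only for the rest. Section 1.1 describes class effects but does not label any as expected in this study.

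**Step 3. Follow one event through each reading.** Take a participant hospitalised with a cardiovascular event that is not fatal.

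| Meaning of *unexpected* in the definition | SAE? | 24-hour form | Sponsor notice |
|---|---|---|---|
| A. Ordinary meaning; event judged a known class effect | No | Not triggered | Not triggered |
| B. Ethics committee bullet's meaning; no list exists | Yes | Triggered | Triggered |
| C. Ethics committee bullet's meaning; a list is added that names the event | No | Not triggered | Not triggered |
| Any of these, with *and unexpected* deleted | Yes | Triggered | Triggered |

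Under B the two words have no effect. Under A and C they remove the event from both reporting routes. Under no reading do they improve reporting to the sponsor.

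**Step 4. Does other text close the gap under A or C?** Only in part.

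- The medical-judgement clause keeps some expected events in, but it is not written for hospitalised or life-threatening ones. Read literally, a milder expected event could count as serious while a hospitalised one does not.
- The general rule names no recipient or deadline and refers on to the specific procedures.
- The statement that events are recorded regardless of expectedness is made for non-serious events only.

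**Step 5. Would the deletion alone bring in every serious event?** No. The Serious AEs paragraph also says that relapse and death, and admissions for elective treatment of an existing condition, need not be reported as SAEs. Death is also the first outcome in the SAE definition. These two statements conflict whatever *unexpected* means.

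**Scale.** The plan is 20 men per arm, 40 in all, with the option of 20 more per arm: 40 + 2 × 20 = 80. Each man may have two 7-day treatment periods. These are numbers randomised, placebo included, and not event counts. The documents give no event rate.

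**The case against.** The strongest reply is reading B. The ethics committee bullet gives the only meaning of *unexpected* in the protocol, and no list of expected events is to be found. On that meaning a serious event of a known NSAID type is unexpected, is an SAE and reaches the sponsor. Read as a whole, Section 5 also points to the usual scheme: it sorts events only into serious and non-serious, and it contrasts sponsor notice of all SAEs with a narrower rule for the ethics committee.

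This stands as an available reading, and it limits the conclusion. A reader might infer that all expected serious events leave the SAE stream. The documents do not support that: reading B keeps them in, and the medical-judgement clause keeps some in under any reading. A reader might also take a hospitalised bleed on celecoxib as the natural example. Section 1.1 does not mention bleeding. It raises gut toxicity for the older NSAIDs and kidney toxicity for ibuprofen, each in comparison with COX-2 selective drugs or celecoxib. Only the cardiovascular effects are presented as class-wide.

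The reply does not make the text safe. The bullet's meaning is neither stated in the definition nor referred to there. It also presupposes a list, and supplying that list would turn reading B into reading C.

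**Conclusion.** The point holds as an internal inconsistency with a possible safety-reporting consequence. Section 5 puts expectedness into the SAE definition and then uses it again as a separate filter. Whether a hospitalised or life-threatening event of a known class type triggers the 24-hour form and the sponsor notice depends on which meaning the investigator applies, and on whether a list of expected events is ever added.

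The loss is neither certain nor complete. It arises under the ordinary meaning or with a list, and not under the ethics committee bullet's meaning without one. Few events are likely in 40 to 80 healthy men treated for 7 days at a time, but this is a judgement, since no rate is given. The conclusion also assumes that the pages not available contain no list and no overriding definition. The change is still worth making, because it corrects a stated rule and protects reporting under every reading.

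**What to change.** 1. Delete *and unexpected* from the SAE definition, so that seriousness rests on the listed outcomes and the medical-judgement clause. Keep *related* and *unexpected* only as the test for ethics committee reporting.
2. In the same amendment, reconcile the sentence that exempts relapse and death from SAE reporting with death as a seriousness criterion. Without this, the deletion does not bring every serious event into the SAE stream.

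The cost is a two-word deletion, one sentence to reconcile, and possibly a few more SAE forms. No dose, visit, endpoint or analysis changes.

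### Section 5 counts death as a serious adverse event and then exempts it from reporting as one

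*Combined protocol and SAP*

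**What the plan says.** Everything relevant is in Section 5, Adverse Events.

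- **Definition.** An SAE is "any untoward and unexpected medical occurrence or effect that" meets one of five listed criteria. The first is "Results in death", with no limit by cause. The others are a threat to life, hospitalisation, disability or incapacity, and congenital anomaly. The threat-to-life criterion "refers to an event in which the subject was at risk of death at the time of the event".
- **Widening by judgement.** Important events that "do not result in death or hospitalisation but may jeopardise the subject" are also to be treated as serious.
- **General rule.** "All adverse events will be reported", with the procedure depending on the nature of the event. Non-serious events are recorded.
- **Serious events.** "A SAE form will be completed and sent to the medically qualified Investigator" within 24 hours. The exemption follows at once: "However, relapse and death and hospitalisations for elective treatment of a pre-existing condition do not need reporting as SAEs".
- **Onward reporting.** SAEs judged related and unexpected go to the ethics committee within 15 days. The Chief Investigator notifies the sponsor of all SAEs. Neither instruction makes an exception for death.

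**The concern.** The definition and the exemption give opposite answers on death. Under the first, a death calls for an SAE form within 24 hours. Under the second, it need not be reported as an SAE. Two members of staff could each follow Section 5 correctly and act differently.

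The literal result is also the wrong way round. A lesser event, serious only by medical judgement, would need the 24-hour form, while a death would not.

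The protocol's own background (Section 1.1) describes cardiovascular warnings on this drug class and a risk that appears within 1-2 weeks of use. Participants randomised to celecoxib take it for 7 days. The documents give no event rate for healthy men aged 18-40, and a death may be very unlikely. Even so, the rule for the most serious outcome should have only one reading.

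**Working it through.** The plan states no figure on this point, so there is none to reproduce. The check is a comparison of wording plus a few counts.

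**1. The direct comparison.** The definition makes death a sufficient criterion, whatever its cause. The exemption names death, also without naming a cause. Unless some other text limits one of them, the two conflict.

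**2. Does the word unexpected limit the definition?** An expected death would fall outside the definition and so could be exempted without conflict. The only meaning Section 5 gives to the word is in the ethics-reporting list: "an event that is not listed in the protocol as an expected occurrence". No text available for review lists death as expected, and the exemption is not confined to expected deaths. The conflict remains.

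**3. Does the reference to a pre-existing condition limit the exemption?** There are two readings.

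- *Broad:* the phrase belongs only to the elective hospitalisations, which is the more natural grammar. Every death is then exempt, and the exemption cancels the first criterion.
- *Narrow:* the phrase limits all three items. Only deaths from a pre-existing condition are then exempt. This works as an exception to the definition, although such a death still meets the first criterion. It would cover very little, because Section 4 excludes significant medical conditions and requires normal findings at screening.

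The mention of relapse does not help to choose between them. The participants are healthy volunteers, with no study disease that could relapse.

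**4. Does other text in Section 5 catch a death anyway?** In part.

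- The general rule requires every adverse event to be reported, but it passes the event on to the procedures that contain the exemption.
- The only other procedure, for non-serious events, requires recording and gives no form, deadline or recipient.
- A fatal event may also meet the threat-to-life criterion. If deaths are exempt from SAE reporting, however, meeting a second criterion does not clearly restore the duty.

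**5. Counts.**

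| Item | Count |
|---|---|
| SAE criteria listed | 5 |
| Touched by the exemption | 2 (death in conflict, hospitalisation narrowed) |
| Untouched | 5 − 2 = 3 |
| SAE reporting steps | 3 (24-hour form, ethics report, sponsor notice) |
| Steps the exemption directly follows | 1 (the form) |
| Remaining steps with their own exception for death | 0 of 2 |
| Items in the exemption | 3 (relapse, death, elective hospitalisation) |
| Items left after deleting relapse and death | 3 − 2 = 1 |

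These counts show how far the conflict reaches in the text. They do not measure the probability of harm.

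**The case against.** The strongest reply is that the exemption concerns reporting and leaves the definition alone. An unexpected death is still an SAE, so the sponsor must be told and, if the death is related, so must the ethics committee. On that view only the 24-hour form is in doubt. This is a fair reading and probably the one intended. But the exemption speaks of reporting as SAEs in general, and a reader could extend it to the two later steps, which are both written for SAEs.

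A second reply is that, on the narrow reading, a general rule followed by a limited exception is ordinary drafting, just like the elective-hospitalisation exemption. That is right as far as it goes: the outright contradiction depends on the broad reading. The broad reading is the more natural one, though, and nothing in the document rules it out.

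Third, Section 5 sends any question on adverse event reporting to the Chief Investigator and the medically qualified investigators first. That gives staff a way to settle the doubt and lowers the practical risk. It does not tell them which sentence governs, and someone who reads only the exemption may see no question to ask.

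Finally, the odd mention of relapse suggests stray wording rather than a policy of leaving deaths unreported. That seems likely, and it bears on how serious the fault is. It does not remove the fault.

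**Conclusion.** The concern holds. As written, Section 5 leaves unclear whether a death triggers the 24-hour SAE form and, if it is not handled as an SAE, whether the sponsor and ethics routes apply. The consequence is modest, and nothing in the design or analysis depends on it. It should be corrected because it concerns participant safety and the sentence is operative text.

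The conclusion rests on two assumptions. One is that the pre-existing condition qualifies only the elective hospitalisations. The other is that no text outside the pages available for review (the opening pages and the part between Sections 8 and 10 were not) lists death as expected or limits the exemption. No event rate is assumed.

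**What to change.** Reconcile the exemption with the definition. The simplest way is to delete four words from the exemption, those naming relapse and death with the conjunction after each. It then covers only hospitalisations for elective treatment of a pre-existing condition, and death follows the same SAE route as the other criteria. If the sponsor did mean to exempt some class of death, the sentence must say which, and the definition and the three reporting steps must be made to agree with it.

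The cost is a short protocol amendment. Visits, sample size, endpoints and analysis do not change.
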